## 5. PARTICIPANTS

### 5.1 Number of Participants

As described in the chapter Sample Size Calculation, a maximum of 93 patients will be included in the trial.

The recruitment will be stopped, if (whatever occurs first)

- 79 patients will have a FDG-PET/CT confirmed stage I/II follicular lymphoma and a trial specific therapy has been initiated or
- 55 patients had a second restaging FDG-PET/CT in week 18 or
- 93 patients were included

Recruitment and treatment of the participating patients will be performed in 15 locations/30 sites (each location consists of a radiation oncology site and a hemato-oncology site).

The sites should have experience in the treatment of early stage follicular lymphoma (min. 5 patients / year). The sites should have the infrastructure for execution and documentation of a clinical trial according the AMG, Röntgenverordnung and Strahlenschutzverordnung. There must be the possibility to conduct a FDG-PET/CT.

Each location should include 6-7 patients. All sites, which successfully recruited and completely documented the therapy and follow-up of at least 4 patients will be considered for authorship in the final publication.

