#### 5.5 Criteria of Withdrawal

##### 5.5.1 Withdrawal of patients from treatment

Any patient can withdraw from the treatment at any time without personal disadvantages and without having to give a reason. Patients who discontinue participation in the clinical study on their own or patients who are withdrawn by the investigator, for reasons other than disease progression (i.e. in case of AEs, protocol violations, ...), will be defined as premature withdrawals. Premature withdrawals will not be replaced.

The investigator can also discontinue the study after considering the risk-to-benefit ratio, if he/she no longer considers the further treatment of the patient according to study protocol justifiable. The date of and the primary reason for the withdrawal, as well as the observations available at the time of withdrawal are to be documented on the CRF. Reasons leading to the withdrawal of a patient can include the following (**one primary reason must be determined**):

- **Lack of efficacy** of the study medication, e.g.
  - Progress of study disease compared to baseline
  - Need for a prohibited concomitant medication for the treatment of study disease
- **Intolerable adverse events**
- **Lack of patient's cooperation**, e.g.
  - Patient's request to withdraw
  - Lack of compliance, patient fails to attend the interim visits as agreed
  - Existing or intended pregnancy, lactation
- **Other reasons** (noting reason), e.g.
  - Other diagnosis than study disease
  - Did not meet major in-/exclusion criteria (coming to light after inclusion)

In all patients who finish the study prematurely, a withdrawal examination at least with respect to the primary endpoint should be carried out. The patient must be asked to consent to this last examination. The withdrawal examination must be documented in the CRF.

In case of a drop-out, all ongoing AEs or SAEs should be monitored until there are no more signs or symptoms or until the participant shows a stable condition.

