### 5.5.2 Definition of drop-outs

Term	Definition
Drop-out, study	
Participation terminated completely, including follow-up
 
Possible reasons:
 
 
• Patient withdraws consent: Withdrawal
 
• Patient moved/cannot be contacted
 
• Follow-up-interventions cannot be performed due to medical reasons
 
• Non-compliance of patient
 
 
Drop-out after completion of study intervention: Lost to follow-up
 
FU-CRF-forms need to be marked as invalid.
 
Final examination will be performed, if patient agrees. Study-Completion/ Withdrawal-form will be completed.

Drop-out, study intervention	Termination of study intervention, follow-up as per protocol.
Screening-failure	
Exclusion criteria given prior to screening / enrolment:
 
Patient will be recorded at screening list, but will not be provided with a patient number.
 
(Depending on sponsor a screening CRF may have to be completed)

Protocol deviation	
Drop-out to study and drop-out to study intervention are both protocol deviations.
 
It needs to be predefined, how to manage each type of protocol deviation.
 
Major deviations:

If exclusion criteria become evident after enrolment, and safety of the participant is affected, or if the diagnosis does not any more relate to the indication listed in the protocol affecting the benefit/risk negatively, the participant has to be excluded from study intervention. FU-examinations may still be performed.

Minor deviations:

Other protocol deviations (errors in timing of visits/ missing samples/ missing examinations) do not result in exclusion

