## 11.2 Variables of analysis

Primary endpoint is the metabolic complete response (CR) in week 18 in patients with initially remaining lymphoma judged by FDG-PET/CT.

Secondary endpoints are:

- Morphologic CR, PR, SD, PD in week 7, week 18 and month 6 in patients with initially remaining lymphoma judged by CT/MRI
- Historical comparison of the morphologic response with MIR data (using MabThera); the comparison of the CR rate in week 7 would be a comparison of the two different CD20 antibodies. Based on the patient numbers no matched pair analysis will be possible
- Progression-free survival (PFS) of all treated patients (2 years after individual treatment start)
- Toxicity (NCI-CTC criteria, version 4.03) of all patients
- Relapse rate and pattern of recurrence of all treated patients at all follow-up visits.
- Overall survival (OS) of all treated patients (2 years)
- Quality of life according EORTC QLQ C30 and FACT-Lym questionnaires at inclusion and in week 18, month 12, 24 and 30 (all treated patients)
- MRD response: initially, week 18, months 12 and month 24 (all treated patients). MRD is evaluated by the laboratory of [name] (Kiel) using at least the markers: t(14:18) PCR for MBR, 3'mbr, 5'mcr and MCR; clonal IGH rearrangements (FR1-3); clonal IGL rearrangements (IGK and Kappa-KDE)

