## 11.3 Definition of the Trial Populations

All patients, who received at least parts of the treatment defined in this protocol, will be analyzed in the intention-to-treat (ITT) population as well as in the safety population. All patients, who deviated less than 20% from the protocol-defined dose and fulfill all inclusion and exclusion criteria, will be analyzed in the per-protocol (PP) population. Efficacy will be evaluated in the ITT- as well as in the PP population. Toxicity data will be analyzed in safety population.

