## 11.4 Statistical Methods

There will be a descriptive analysis of the data. The rate of metabolic CR in week 18 will be calculated as relative frequency. The related 95% confidence interval will be calculated using the "score method" by Wilson [65]. This method showed excellent performance characteristics as compared to alternative

approaches of constructing confidence intervals for rates [64]. In addition, the rate of metabolic CR will be estimated using the Kaplan-Meier method and the 95% Greenwood confidence interval to take into account a potential influence of censored values. (ITT and PP population)

PFS and OS at 2 years after initiation of the therapy of each patient will be analyzed using the Kaplan-Meier method and the two-sided 95% confidence intervals according to Greenwood. (ITT and PP population).

Remission- and recurrence rates will be calculated as relative frequencies and reported together with the 95% confidence intervals according to Wilson. (ITT and PP population)

Quality of life will be evaluated according to the evaluation guide of the two questionnaires. (ITT and PP population)

Toxicity will be evaluated for frequency and intensity (safety population). Adverse events will be coded by MedDRA (actual version at the time of data base lock). The counts of the events and the counts of patients will be listed in a table. All patients under observation will be taken into account for the calculations of the frequency of recurrences at the respective time.

All statistical procedures will be defined in a statistical analysis plan (SAP), which will be finalized before data base lock. The responsible statistician and the LKP will authorize the SAP.

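### Section 11.4 computes recurrence as a simple proportion of patients under observation, although the endpoint covers all treated patients; censoring, the numerator and the status of recurred patients are left open

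*Combined protocol and SAP*

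**What the plan says.** Sections 2.3 and 11.2 list as a secondary endpoint: "Relapse rate and pattern of recurrence of all treated patients at all follow-up visits". Section 11.3 defines the analysis set: "All patients, who received at least parts of the treatment defined in this protocol, will be analyzed in the intention-to-treat (ITT) population".

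Section 11.4 gives the estimator: "Remission- and recurrence rates will be calculated as relative frequencies and reported together with the 95% confidence intervals according to Wilson", for both the ITT and the PP population. At the end of its paragraph on toxicity it adds the denominator rule: "All patients under observation will be taken into account for the calculations of the frequency of recurrences at the respective time".

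The same section uses Kaplan-Meier with Greenwood intervals for two-year PFS and OS. It also adds a Kaplan-Meier estimate for the week-18 metabolic CR rate, expressly because of possible censoring. Recurrence gets no such treatment. Details are deferred to a statistical analysis plan to be finalised before database lock.

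On who remains observed:

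- Section 5.5.1, on withdrawal from treatment, gives as an example of lack of efficacy: "Progress of study disease compared to baseline".
- Section 5.5.2 separates stopping the intervention ("Termination of study intervention, follow-up as per protocol") from leaving the study ("Participation terminated completely, including follow-up"). Recurrence is not among the possible reasons it lists for leaving the study.

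**The concern.** A rate in all treated patients and a rate in patients under observation at a visit are different quantities once anyone has been lost. Section 11.4 asks for the second under the label of the first. Two further choices are missing: whether the numerator is all recurrences so far or only those new at the visit, and whether a patient who has recurred remains under observation. Two statisticians could follow the text faithfully and report clearly different month-24 rates.

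The endpoint carries weight although it is secondary and descriptive. Section 1.3 accepts that low-dose radiotherapy has a higher recurrence risk than a higher dose. Section 2.1 asks for the site of recurrence in three PET-defined subgroups. With the planning figures of 11.1, the group that becomes PET-negative at week 18 would have about 0.60 × 50 = 30 patients, so one patient counted differently moves its rate by about 1/30 = 3.3 points. A rule that understates recurrence would make the dose reduction look safer than it is.

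**Working it through.** **The plan's own figures.** The documents give no expected recurrence rate. The planning figures in 11.1 reproduce: the half-width is 1.96 × √(0.6 × 0.4 / 50) = 13.6 points (stated as about 13.5), and the number of treated patients is 93 × 0.85 = 79.

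**Inputs for the illustration**

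- N = 79 treated, the maximum in 5.1.
- True two-year recurrence 14%. This is an assumption: section 1.1.5 gives 86% two-year PFS in the MIR trial, and all events are treated as recurrences. Range examined: 14% to 30%.
- Drop-out 10% by month 24. This is also an assumption: 11.1 plans 10% for the primary endpoint. Range examined: 5% to 20%.
- Constant, independent hazards.

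**Formulas.** With S = 0.86 and d = 0.10:

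- Still observed and recurrence-free at month 24: G = S(1 − d) = 0.774, or 61.1 patients.
- Share of first events that are recurrences: ln S / (ln S + ln(1 − d)) = 0.1508 / 0.2562 = 0.589.
- Recurrences observed by month 24: 0.589 × (1 − 0.774) = 0.133, or 10.5 patients.
- Of these, new in months 18–24: 0.589 × (0.774^0.75 − 0.774) = 0.030, or 2.4 patients.

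**Month-24 rate by reading (true value 14.0%)**

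| Reading | Calculation | Result | Drop-out 5–20% |
|---|---|---|---|
| Recurred patients stay in numerator and denominator | 10.5 / (10.5 + 61.1) | 14.7% | 14.3–15.5% |
| Recurred patients leave the denominator, stay in the numerator | 10.5 / 61.1 | 17.2% | 16.7–18.3% |
| Earlier recurred patients leave both, only new recurrences count | 2.4 / (2.4 + 61.1) | 3.7% | 3.7–3.8% |

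The first row assumes that nobody is lost after recurring. If recurred patients are lost at the same rate as the others, the proportion among those observed is (79 × 0.14 × 0.90) / (79 × 0.90) = 14.0%, with no error. Dividing observed recurrences by all treated patients gives 10.5 / 79 = 13.3%, slightly low because of the losses.

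**Scale.** The Wilson interval for 11 of 79 is 8.0% to 23.2%, so the first-row error of 0.7 points lies well inside sampling noise. On the third reading the count would be about 2 of 63 or 3 of 64. The Wilson intervals are then 0.9–10.9% and 1.6–12.9%, and neither contains 14%.

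**Higher recurrence, drop-out 10%.** At a true 20% the three readings give 20.9%, 26.4% and 5.5%. At a true 30% they give 31.2%, 45.3% and 8.6%.

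**Which reading do the documents support?**

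- For staying counted: 5.5.1 concerns treatment, 5.5.2 continues follow-up after the intervention stops, and two-year OS in all treated patients needs follow-up beyond recurrence.
- For leaving: the definition of premature withdrawal in 5.5.1 sets progression apart from other reasons for ending participation. Section 9 mentions treatment of a recurrence under care after the trial, including early ending. Section 13.6 bars other clinical treatment during the trial except in emergencies.
- The follow-up clause in 5.5.2 does not clearly settle later recurrences. Antibody ends in week 16 and salvage radiotherapy by week 23 or 24, so a patient recurring at month 12 has no study intervention left to stop.

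The question stays open.

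**The case against.** A reader might infer that the month-24 rate will be badly wrong in one direction or the other, because recurrence takes patients out of the denominator. The documents do not support that. The sentence in 11.4 does not say that only patients under observation count, and it does not say that a recurred patient ceases to be under observation. Progression appears as a possible reason for withdrawal from treatment, not as a compulsory exit from follow-up. In the illustration about 72% of recurrences (7.6 of 10.5) fall after month 6, when no trial treatment remains to be withdrawn from. On the reading closest to 5.5.2 the error is under one point.

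The figure of about 4% is also an interval incidence. It needs a numerator that the plan does not state, so its distance from 14% is not the bias of a planned estimator. The 17% figure likewise needs a rule that is not written.

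Finally, Kaplan-Meier PFS already gives a censoring-aware two-year estimate, the trial is descriptive, and the analysis plan can still define details.

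These objections remove the claim of certain, large error. They leave the mismatch between the two denominators, the missing numerator and the lack of a censoring method. PFS does not fill the gap, because it combines death with progression and does not separate in-field from out-of-field recurrence. The later analysis plan has to implement 11.4, whose wording is inconsistent with the endpoint.

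**Conclusion.** The point holds as an inconsistency in the estimator for a secondary endpoint that should be corrected. The denominator in 11.4 does not match the endpoint in 2.3 and 11.2 or the ITT set in 11.3, and a simple proportion ignores censoring that the same section handles for PFS, OS and week-18 CR.

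The size is conditional. Under the assumptions above, the month-24 error is at most about 0.7 points if recurred patients stay counted, and up to 1.5 points at 20% drop-out. It is about 3 points upward if they leave the denominator only. A reported value near 4% against 14% arises only if they leave both and only new recurrences count. The larger figures show what the wording permits, not what will happen. All rest on the MIR PFS as a proxy for freedom from recurrence and on drop-out extended to month 24.

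**What to change.** In 11.4 and the statistical analysis plan, replace the denominator sentence with a rule to this effect: recurrence (overall, in-field and out-of-field) is reported as cumulative incidence from start of therapy in all treated patients at months 6, 12, 18, 24 and 30. Death without recurrence is a competing event. Patients without recurrence are censored at their last assessment. Patients who have recurred keep their event, whatever their later follow-up status. A descriptive proportion with a Wilson interval may stand alongside if its numerator and denominator are stated.

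Sections 5.5.1, 5.5.2, 9 and 13.6 should be reconciled so that the follow-up status of a patient after recurrence is unambiguous. Which status applies is for the sponsor to decide; the estimator above keeps the event either way.

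The cost is wording only. The event and assessment dates are those already needed for PFS, and recurrence site is already part of the endpoint. The downside is a slightly more complex estimator for a descriptive secondary endpoint.

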### 11.5 Interim Analysis

No interim analysis is planned.

### 11.6 Definition of Target Variables

Progression-free survival:

- a) Calculated from start of therapy up to the time of progression (morphologic or metabolic) or death
- b) Calculated from start of therapy up to the time of progression (morphologic or metabolic) or death in patients with initially remaining lymphoma (morphologic or metabolic)

Overall survival:

Calculated from start of therapy up to the time of death

## 12. DATA MANAGEMENT

### 12.1 Data Collection

All entries in the CRF must be verifiable by source documents. In advance, exceptions to this rule can be defined by the sponsor. A detailed list will be provided in the Investigator Site File. Regardless, there must be a minimum documentation, which provides information on study participation and includes all medical information necessary for appropriate medical care outside of the clinical trial in the patient record.

In addition, source documents must mention that the patient has been included in an investigational study. Finally, there must be no data that are inconsistent between CRF and source documents.

The investigator is responsible for ensuring that all sections of the CRF are completed correctly and that entries can be verified against source data. Any errors should have a single line drawn through them so that the original entry remains legible and the correct data should be entered at the side with the investigator's signature, date and reason for change. Self-explanatory corrections need not to be justified.

The correctness of entries in CRF will be confirmed by dated signature of the responsible investigator. The original CRF will be transferred to the data management in the Institute of Medical Biometry and Informatics (IMBI) Heidelberg; one copy will be remained by the investigator.

## 12.2 Data Handling

All data will be entered in a database as recorded in the CRF by trained staff of the IMBI. To ensure data quality, a double data entry will be done. The data management will check completeness, validity, and plausibility of data by validation programs, which will generate queries.

All missing data or inconsistencies will be reported back to the centre(s) and have to be clarified by the responsible investigator prior to database lock. If no further corrections are to be made in the database it will be declared locked and used for statistical analysis.

All data management activities will be done according to the current SOPs of the IMBI.

Original files of the CRF will be transferred to the LKP after analysis and completion of the trial report.

## 12.3 Archiving of Essential Documents

The investigator(s) will archive all trial data (source data and Investigator Site File (ISF) including subject identification list and relevant correspondence) according to the section 4.9 of the ICH Consolidated Guideline on GCP (E6) and to local law or regulations.

The sponsor or other owner like investigators of the data shall retain all other documentation pertaining to the trial for at least 10 years according to the §13 of the German GCP-Ordinance. These procedures shall include:

- The protocol including the rationale, objectives and statistical design and methodology of the trial, with conditions under which it is performed and managed, and details of the investigational product used.
- Standard operating procedures
- All written opinions on the protocol and procedures,
- Final report,
- Case report forms (not RDE),
- Audit certificate(s), if available.
- All other relevant documents of the trial master file, according to the ICH-GCP guideline

Any change of data ownership shall be documented. All data shall be made available if requested by relevant authorities.

According to the §28c of the German X-Ray Directive and to the §87 of the German Radiation Protection Directive the informed consent forms including subjects' consent for trial participation, application of x-rays, application of radioactive materials or irradiation and data transmission to the competent authority will be archived for at least 30 years after the trial termination.

The LKP is responsible for archiving of the trial master file (TMF). It will be archived according the SOP for archiving of the University Hospital of Heidelberg.

The investigator will archive all study documents including patient identification list and relevant correspondence in the Investigator Site File (ISF). The ISF, all source documents as well as all other in section 8 of the 'ICH Consolidated Guideline on GCP' listed documents are to be stored and archived after the regular or early ending of the trial according to the legal regulations.

## 13. ETHICAL AND LEGAL ASPECTS

### 13.1 Good Clinical Practice

The procedures set out in this trial protocol, pertaining to the conduct, evaluation, and documentation of this trial, are designed to ensure that all persons involved in the trial abide by ICH harmonised tripartite guideline on Good Clinical Practice (ICH-GCP) and the ethical principles described in the applicable version of the Declaration of Helsinki. The trial will be carried out in keeping with local legal and regulatory requirements.

The regulations of the AMG and GCP regulations as well as the Bundesdatenschutzgesetz (BDSG) will be respected.

### 13.2 Legal Bases

The study has to be conducted in compliance with the protocol, ICH-GCP and the applicable regulatory requirements

#### 13.2.1 Declaration of Helsinki

The procedures set out in this trial protocol, pertaining to the conduct, evaluation, and documentation of this trial, are designed to ensure that all persons involved in the trial abide by ICH harmonised tripartite guideline on Good Clinical Practice (ICH-GCP) and the ethical principles described in the applicable version of the Declaration of Helsinki. The trial will be carried out in keeping with local legal and regulatory requirements.

#### 13.2.2 Other legal bases

The other legal bases of this clinical trial are as follows:

- ICH Topic E6, Guideline for Good Clinical Practice, including post Step 4 errata, September 1997
- Directive 2001/20/EC (April 4, 2001)
- Commission Directive 2005/28/EC (April 8, 2005)
- National regulatory requirements/guidelines of the participating countries concerning Clinical Trials [e.g. federal drug law (AMG), GCP ordinance (GCP-Verordnung)]
- Valid version of the Radiation Protection Ordinance / Röntgenverordnung
- General national regulatory requirements, e.g. Bundesdatenschutzgesetz (BDSG)

The Coordinating Investigator and all investigators will be given an up-to-date investigator's brochure containing full details of the status of the pre-clinical and clinical knowledge of the study medication. As soon as new information is obtained, an updated version will be supplied or an amendment added to the existing investigator's brochure.

